3.2.3.2 Clinical Laboratory Tests

The following safety laboratory parameters will be measured:

- **Hematology:** Leukocytes and leukocyte differential count (percentage values and absolute values), erythrocytes, hemoglobin, hematocrit, MCV, MCH, MCHC, thrombocytes.
- **Biochemistry:** sodium, potassium, calcium, chloride, inorganic phosphorus, alkaline phosphatase, γ -GT, AST, ALT, total bilirubin, creatinine, glucose, urea or BUN, uric acid, total cholesterol, triglycerides, total proteins.
- **Urinalysis:** pH, specific gravity, appearance, color, nitrites, proteins, glucose, urobilinogen, bilirubin, ketones, leukocytes, erythrocytes, epithelial cells, crystals, cylinders.

Overall investigator's interpretation (as normal or abnormal and, if abnormal, clinically significant [NS] or not clinically significant [NCS]) and clinically significant findings (if any) will be reported in the individual eCRFs. All CS abnormalities after the screening visit will be recorded as AEs.

3.2.3.3 Vital Signs

The following vital signs measurements will be obtained:

- Systolic blood pressure (SBP) [mmHg]
- Diastolic blood pressure (DBP) [mmHg]
- Heart rate (beats/min)

3.2.3.4 Body Weight

3.2.3.5 12-Leads Electrocardiograms (ECGs)

The ECG recording will be evaluated by the Investigator as ‘Normal’, ‘Abnormal, NCS’ or ‘Abnormal, CS’.

All CS abnormalities after the screening visit will be recorded as AEs.

3.2.3.6 Physical Examination

Full physical examinations will be performed, overall investigator’s interpretation (as normal or abnormal and, if abnormal, CS or NCS) and CS abnormalities (if any) will be reported in the individual eCRFs.

All CS abnormalities after the screening visit will be recorded as AEs.

4 STATISTICAL METHODS

4.1 Data Quality Assurance

All tables, figures and data listings to be included in the report will be independently checked for consistency, integrity and in accordance with standard PAREXEL procedures.

4.2 General Presentation Considerations

Each cohort has three periods (pre-treatment period, single dose period (Day 1) and multiple doses period (Day 8 to Day 18)) with a washout duration of 7 days between single dose period and multiple dose period. Period will be displayed for subject listings where applicable. ‘Baseline’ is defined as the last available assessment prior to the first dose of study treatment (per period when pre-dose assessment is available for both of the single dose and multiple dose periods). ‘End of Study’ is defined as the last available post-treatment assessment. ‘Study Day’ will be calculated relative to the first dose date of study treatment i.e. Study Day = Assessment Date -First Dose Date + 1 (+ 1 if assessment date is on or after the first dose date).

Continuous data will be summarized in terms of the mean, standard deviation (SD), coefficient of variation (CV) (%), median, minimum, maximum and number of observations, unless otherwise stated.

Continuous data that are expected to be skewed will be presented in terms of the maximum, upper quartile, median, lower quartile, minimum and number of observations. The minimum and maximum will be reported to the same number of decimal places as the raw data recorded in the database. The mean, median, lower quartile and upper quartile will be reported to one more decimal place than the raw data recorded in the database. The SD will be reported to two more decimal places than the raw data recorded in the database. The CV(%) will be presented to one decimal place. In general, the maximum number of decimal places reported shall be four for any summary statistic.

Categorical data will be summarized in terms of the number of subjects providing data at the relevant time point (n), frequency counts and percentages. Any planned collapsing of categories will be detailed in the SAP text and the data displays.

Percentages will be presented to one decimal place. Percentages will not be presented for zero counts. Percentages will be calculated using the number of subjects included in the corresponding set of subjects that is indicated in the title of the tables as the denominator. If sample sizes are small, the data displays will show the percentages, but any textual report will describe frequencies only.

Changes from baseline in categorical data will be summarized using shift tables where appropriate.

4.3 Software Considerations

All report outputs will be produced using SAS® version 9.3 or a later version [4] in a secure and validated environment.

The PK parameters will be produced using Phoenix® WinNonLin (WNL) version 8.0 [5] in a secure and validated environment.

All report outputs will be provided to the Sponsor in RTF and/or PDF format.

4.4 Study Subjects

4.4.1 Disposition of Subjects

A subject will be defined as screened after the signature of the informed consent, regardless of the completion of all the screening procedures. A subject will be defined as eligible if he/she meets all the inclusion criteria and not meet any exclusion criteria. Otherwise he/she will be defined as a

screen failure. A subject will be defined as enrolled in the study if he/she is included into the interventional phase of the study. The enrollment will be performed through randomized allocation to a treatment cohort. An eligible but not enrolled subject will be defined as a reserve. A subject will be defined as randomized in the study when he/she is assigned to a randomized treatment cohort. A clear accounting of the disposition of all subjects who enter the study will be provided, from screening to study completion.

- A summary of the number of subjects screened for entry into the study and the number and percentage of eligible subjects, screen failure subjects (including the reason for screen failure), enrolled subjects, and randomized subjects.
- A summary of the number of subjects randomized, the number and percentage of subjects treated (with at least one dose of study medication) and the number and percentage of subjects withdrawing from study treatment and withdrawing from the study by treatment cohort and overall. Withdrawals from the study and from study treatment should also be summarized by major reason. Primary reason of study discontinuation or study treatment discontinuation will be documented as one of the following:
 - Adverse event
 - Death
 - Lost to follow-up
 - Non-compliance with study drug
 - Physician decision
 - Pregnancy
 - Protocol deviation
 - Study terminated by sponsor
 - Technical problem
 - Withdrawal by subject
 - Other

By-subject listings of eligibility details, randomization details and study treatment/study discontinuation/completion details (including reason for discontinuation) will be provided.

4.4.2 Protocol Deviations

All protocol deviations will be recorded by the Investigator. Major protocol deviations are defined as those deviations from the protocol that are likely to have an impact on the subject's rights, safety, well-being, and/or on the validity of the data for analysis. The impact of major protocol deviations will be investigated by assessing the robustness of the study results and conclusions to the choice of analysis set, both including and excluding data potentially affected by major protocol deviations.

Major protocol deviations and any action to be taken regarding the exclusion of subjects or affected data from specific analyses are defined in the project-specific Protocol Deviation Specification and approved by Sponsor. All major protocol deviations will be discussed between PAREXEL and the Sponsor during the data review meeting shortly before database lock in order to determine whether these may warrant exclusion of a subject from the statistical analyses. Results and population assignments will be summarized in a meeting minute/report and will be signed off by all relevant scientific experts.

- A summary of the number and percentage of subjects with a major (approved by sponsor) protocol deviation by treatment cohort and overall

A by-subject listing of major protocol deviations should be provided.

4.5 Analysis Sets

The number and percentage of subjects within each analysis set will be summarized based on all enrolled subjects. A by-subject listing, including the reasons of being excluded from a specific analysis set, will also be provided.

4.5.1 Randomized Set

The randomized set includes all subjects randomized. This analysis set will be used for the analysis of demographic, baseline and background characteristics. If a subject is allocated to the incorrect treatment cohort as per the study randomization list, the subject will be summarized and analyzed 'as randomized' i.e. by randomized treatment cohort.

4.5.2 Safety Set

The safety set includes all randomized subjects who receive at least one dose of IMP. Safety analyses will be based on the treatment cohort actually received, not on the treatment cohort to

which the subject was randomized. The safety summaries and analyses will be based on the Safety Set.

4.5.3 Pharmacokinetic Set

The PK Set will include all randomized subjects who fulfil the study protocol requirements in terms of IMP intake and have evaluable PK data readouts, with no major deviations that may affect the PK results. Any data excluded will be discussed at data review meeting before database lock. PK analyses will be based on the treatment cohort actually received, not on the treatment cohort to which the subject was randomized. The PK summaries and analyses will be based on the PK set.

Subjects may/will be excluded (depending on the protocol and IMP under study) from PK set if any of the following criteria are fulfilled:

Before statistical analysis

- Vomiting and diarrhea after drug intake which could render the plasma concentration-time profile unreliable.
- Intake of concomitant medications which could render the plasma concentration-time profile unreliable.
- AEs which could render the plasma concentration-time profile unreliable.
- Administration errors which could render the plasma concentration-time profile unreliable.
- Other events which could render the plasma concentration-time profile unreliable.

After bioanalysis

Subjects can be excluded from PK set only for the reason below:

- Subject with non-zero baseline concentrations $> 5\%$ of C_{max} for single dose and first multiple dose (day 1 and day 8).

The samples from the subjects excluded from the PK set should still be assayed and the results listed. Subjects should not be excluded from the PK set if the AUC_{0-t} covers less than 80% of the $AUC_{0-\infty}$.

4.6 Demographics and Baseline Characteristics

The summaries and listings that will be provided include the following:

- demographic variables (age, sex, ethnicity, height, weight, and body mass index [BMI]) by treatment cohort and overall
- other possibly relevant variables (drug, alcohol, caffeine, and smoking history) by treatment cohort and overall
- other baseline characteristics (virology, pregnancy test, urine drug test, alcohol breath test)

4.7 Medical and Surgical History

All medical and surgical history will be coded using the MedDRA version 22.0.

All medical and surgical history will be summarized by System Organ Class (SOC) and Preferred Term (PT) for each treatment cohort and listed by subject using the safety set.

4.8 Prior and Concomitant Medications

Medication start and stop dates will be compared to the date of first dose of study medication to allow medications to be classified as either Prior, or Concomitant.

Medications that start and stop prior to the date of first dose of study medication will be classified as Prior. If a medication stops on or after the date of first dose of study medication, then the medication will be classified as Concomitant.

If medication start and/or stop dates are missing or partial, the dates will be compared as far as possible with the date of first dose of study medication. Medications will be assumed to be Concomitant, unless there is clear evidence (through comparison of partial dates) to suggest that the medication stopped prior to the first dose of study medication. If there is clear evidence to suggest that the medication stopped prior to the first dose of study medication, the medication will be assumed to be Prior.

Prior and concomitant medication will be coded using the WHO Drug Global Version Mar 2019 or later and will be classified by Anatomical Therapeutic Chemical (ATC) categories.

All prior/concomitant medications will be summarized by ATC level 3 term and PT for each treatment cohort and listed by subject using the safety set.

Information of concomitant procedures, including any surgical, therapeutic or diagnostic procedures, will only be collected for adverse events and serious adverse events, and will be coded using the MedDRA version 22.0. All concomitant procedures will be summarized by SOC and PT for each cohort and listed by subject based on the safety set.

4.9 Treatment Exposure / Compliance

Study treatment will be administered under the supervision of investigator site personnel. The date and time of IMP administration will be listed by subject using the safety set.

4.10 Pharmacokinetics Evaluation

4.10.1 Pharmacokinetics Concentrations

Pharmacokinetic concentration data for will be listed by subject including nominal sampling times relative to cohort/period/day based on PK set. Plasma concentrations below the lower limit of quantification (LLOQ) will be presented as BLQ in the listings. Plasma concentrations will be summarized by dose cohort, period, day and nominal timepoint. The following descriptive statistics will be presented for plasma concentrations obtained at each nominal time point: n, arithmetic mean, SD, coefficient of variation (CV%), geometric mean, geometric CV% (calculated as: $gCV\% = \text{SQRT}(\exp(s^2)-1)*100$; where s is the standard deviation of the log-transformed values), median, minimum and maximum values.

The following rules will be followed with regards to the number of decimal places and presentation of data in the tables and listings of concentration data:

- Source data shall be used in all PK concentrations without prior rounding
- The mean, standard deviation (SD), geometric mean and median will be tabulated to one more significant digit compared to the source data, but with a maximum of four significant digits.
- Minimum and maximum values will be tabulated to the same precision as the source data, but with a maximum of four significant digits.
- Geometric coefficient of variation (gCV) % and coefficient of variation (CV%) will be presented to one decimal place.

Individual plasma concentration versus actual times will be plotted by cohort/period/day in linear and semi-logarithmic scale. Mean plasma concentrations (\pm SD) versus nominal times will also be presented in linear and semi-logarithmic scale.

4.10.1.1 Handling of Values Below the Limit of Quantification (BLQ)

Graphical Presentation

For graphs of arithmetic means all BLQ concentrations will be substituted by zeros. For graphs of geometric means, BLQ concentration values at pre-dose, at all timepoints up to the first quantifiable concentration, between quantifiable concentrations and after the last quantifiable concentration will be substituted by zero, hence geometric means are not defined and disregarded from displays.

Handling of values below the limit of quantification (BLQ) in listings and for the calculation of descriptive statistics at each time point:

- All concentrations below the limit of quantification (BLQ) or missing data will be labeled as such in the concentration data listings. Missing samples will be reported as no sample ("NS") and excluded from analysis. Values that are BLQ will be substituted with zero for the calculation of descriptive statistics of concentration by time point.

4.10.2 Pharmacokinetic Parameters

Pharmacokinetic parameters will be calculated by non-compartmental analysis methods from the concentration-time data using Phoenix® WinNonlin® (Version 8.0). Please refer to section 3.2.2.

Pharmacokinetic parameters will be listed by subject and summarized by cohort, period, and day. Descriptive statistics for calculated PK parameters will include: n, arithmetic mean, SD, CV%, geometric mean, geometric CV%, median, minimum and maximum values. For t_{max} , only median, minimum and maximum values will be presented. No descriptive statistics will be determined when fewer than three individual PK parameters are available.

The following rules will be followed with regards to the number of decimal places and presentation of data in the tables and listings for PK parameters:

- Individual PK parameters will be presented to four significant digits, with the exception of t_{max} , which will be presented to two decimal places.

- Parameters derived directly from source data (e.g. C_{max}) shall be reported with the same precision as the source data (if this is not four significant digits).
- The mean, geometric mean, median and SD values will be reported to four significant digits, all other descriptive statistics will be reported to three significant digits except for CV% which will be presented to one decimal place.
- For t_{max} the minimum and maximum will be presented to two decimal places and all other descriptive statistics will be presented to three decimal places.

4.11 Safety Evaluation

All safety summaries and analyses will be based upon the Safety Set as defined in Section 4.5.

4.11.1 Adverse Events

All AE data will be listed individually by subject. Only TEAEs will be included in the summary tables. Any PTAEs will be included in the data listings but will not be included in the summary tables of AEs.

AEs will be summarized on per-subject basis and per-event basis. A per-subject basis means that even if a subject reported the same event repeatedly (i.e., events mapped to the same PT) during the trial period, the event will be counted only once. A per-event basis will report the number of events.

An overview table will be summarized for the following categories:

- Any TEAEs
- Any TEAEs related to study drug
- Any severe TEAEs
- Any severe TEAEs related to study drug
- Any TEAEs leading to drug interruption
- Any TEAEs leading to drug withdrawal
- Any TEAEs with outcome of death
- Any TEAEs with outcome of death, related to study drug
- Any SAEs (including events with outcome of death)

- Any SAEs (including events with outcome of death), related to study drug
- Any SAEs leading to drug withdrawal

The following summaries will be produced:

- A summary of TEAEs by SOC, and PT
- A summary of TEAEs by PT
- A summary of the most common TEAEs by PT (reported by > 5% of subjects in any treatment cohort).
- A summary of TEAEs by seriousness, SOC and PT
- A summary of TEAEs by severity, SOC and PT
- A summary of TEAEs by causality, SOC and PT

AE summaries will be displayed by period (single dose and multiple dose) and ordered in terms of decreasing frequency in total column for SOC and PT within SOC, and then alphabetically by SOC and PT within SOC. For each subject and each adverse event, the worst severity recorded will be attributed and used in the by-severity summary. Similarly, the worst seriousness will be attributed and used in the by seriousness summary, the worst causality (most related to treatment) will be attributed and used in the by-causality summary. If severity, seriousness or causality is missing, no imputation will be applied.

A by-subject listing of all adverse events (including non-treatment-emergent events) will be provided. This listing will include: subject identifier, age, sex, ethnicity, treatment cohort, period, adverse event (SOC, PT, and verbatim term), start date, end date, severity, causality, seriousness, action taken, and outcome.

4.11.2 Deaths, Serious Adverse Events, and Other Significant Adverse Events

Other significant adverse events are those adverse events reported as leading to drug interruption, drug withdrawal, or study discontinuation.

The following by-subject listings will be produced (if applicable):

- A listing of AEs leading to drug interruption
- A listing of AEs leading to drug withdrawal

- A listing of AEs leading to study discontinuation
- A listing of SAEs
- A listing of all deaths

Listings should follow the format described for AEs in Section 4.11.1 if appropriate.

4.11.3 Clinical Laboratory Evaluation

Summaries will be presented for the overall interpretation of the laboratory data. The number and percentages of subjects within each of the interpretation categories (Normal, Abnormal Not Clinically Significant, Abnormal Clinically Significant) will be summarized in these tables.

By-subject listings of all laboratory data will be provided including: subject identifier, age, sex, ethnicity, weight and visit. Laboratory reference ranges should also be listed. All values outside the clinical reference ranges will be flagged in the data listings. The abnormal values will be flagged with 'L' for values below the lower limit of the clinical reference range and 'H' for values above the upper limit of the clinical reference range and included in the listings.

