10.2 Clinical laboratory assays

Samples of blood and urine will be collected. The following laboratory analyses will be performed at the screening visit:

HAEMATOLOGY

Leukocytes and leukocyte differential count (percentage values and absolute values), erythrocytes, haemoglobin (conv. units), haematocrit, MCV, MCH, MCHC, thrombocytes.

BLOOD CHEMISTRY

Electrolytes: sodium, potassium, calcium, chloride, inorganic phosphorus

Enzymes: alkaline phosphatase, γ -GT, AST, ALT

Substrates/metabolites: total bilirubin, creatinine, glucose, urea or BUN, uric acid, total cholesterol, triglycerides

Proteins: total proteins

Serum pregnancy test (women).

URINE ANALYSIS

Urinalysis: pH, specific gravity, appearance, colour, nitrites, proteins, glucose, urobilinogen, bilirubin, ketones, leukocytes, erythrocytes, epithelial cells, crystals, cylinders.

SERUM VIROLOGY

Hepatitis B (HBs antigen), **Hepatitis C** (HCV antibodies), **HIV 1/2** (HIV Ag/Ab combo).

A urine drug test will be performed at the clinical centre at screening, using a urine multi-drug kit. The following drugs will be assessed: cocaine, amphetamine, morphine, cannabis, benzodiazepines, barbital.

A serum pregnancy test will be performed by the laboratory at screening, as listed above. Urine pregnancy test will be performed on day -1 of each study period at the clinical centre and at the final visit/ETV.

The same analyses, with the exception of urine drug test and virology, will be performed at the final visit/ETV.

Date/time of samples collection, overall investigator's interpretation (as normal or abnormal and, if abnormal, clinically significant or not clinically significant) and clinically significant findings (if any) will be reported in the individual eCRFs. All clinically significant abnormalities after the screening visit will be recorded as AEs.

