13.5.3 Laboratory data

Date/time of samples collection, overall investigator's interpretation (as normal or abnormal and, if abnormal, clinically significant or not clinically significant) and clinically significant findings (if any) will be listed. All laboratory results will be listed and a table of all the abnormal values will be presented.

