4.11.3 Clinical Laboratory Evaluation

For by-visit summaries, the last non-missing assessment (including repeat assessments) recorded at each visit will be summarized. If visit windows are to be used, the non-missing assessment closest to the mid-point of the visit window will be summarized (including repeat and unscheduled assessments). For across visit summaries (e.g. maximum post-baseline value), scheduled, unscheduled and repeat assessments will be considered.

Overall investigator's interpretation (as normal or abnormal and, if abnormal, CS or NCS and clinically significant findings (if any) will be reported in the individual eCRFs. All CS abnormalities after the screening visit will be recorded as AEs.

PAREXEL International
Statistical Analysis Plan for Early Phase Studies

Zambon SpA
Z7219J03

Statistical Analysis Plan

Following summaries will be produced:

- A summary of value and changes from baseline for each laboratory parameter by time point
- A summary of the number and percentage of subjects experiencing low, normal or high values at baseline and at post-baseline time points, for selected laboratory parameter (shift table)

A by-subject listing of all laboratory data should be provided, with abnormal values highlighted, and including: subject identifier, age, sex, race, weight and visit. Laboratory reference ranges should also be listed.

Laboratory values (hematology, biochemistry and urinalysis) will be listed by subject and time point including changes from baseline (with the exception of urinalysis).

All values outside the clinical reference ranges will be flagged in the data listings. The abnormal values will be flagged with 'L' for values below the lower limit of the clinical reference range and 'H' for values above the upper limit of the clinical reference range and included in the listings. The Investigator will assess the values outside the clinical reference range and these will be reported as abnormal NCS or abnormal CS.

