1 INTRODUCTION

The present study will be part of safinamide registration package in China and was designed according to Chinese Food and Drug Administration (CFDA) guideline recommendations [1]. Safinamide has been granted marketing authorization in EU (2015), US (2017) and Switzerland (2015).

The α -aminoamide derivative safinamide [(S)-(+)-2-[4-(3-fluorobenzyloxy) benzylamino] propanamide], developed as methane sulfonate salt, is an original anticonvulsant and antiparkinson agent which has been granted marketing authorization in 9 EU Member States (i.e. Germany, Italy, Spain, Portugal, United Kingdom, Belgium, The Netherlands, Sweden and Denmark), in Norway and in Switzerland under the brand name of Xadago[®], 50 and 100 mg, film-coated tablets [2], for the treatment of adult patients with idiopathic Parkinson's disease (PD) as add-on therapy to a stable dose of Levodopa (L-dopa) alone or in combination with other PD medicinal product in mid-to late-stage fluctuating patients [3].

In the present study, safinamide pharmacokinetic profile, safety and tolerability after single dose and at steady state will be investigated for the first time in Chinese healthy male and female volunteers.

The Statistical Analysis Plan (SAP) details the statistical methodology to be used in analyzing study data and outlines the statistical programming specifications for the Tables, Listings and Figures (TLFs). It describes the variables and populations, anticipated data transformations and manipulations and other details of the analyses not provided in the Clinical Study Protocol (CSP).

The analyses described in this SAP are based upon the following study documents:

- Study Protocol, Version 2.0 (April 18, 2019)
- electronic Case Report Form (eCRF), Version 1.0 (May 7, 2019)

The SAP will be finalized prior to database lock and describes the statistical analysis as it is foreseen when the study is being planned. If circumstances should arise during the study rendering this analysis inappropriate, or if improved methods of analysis should arise, updates to the analyses may be made. Post database lock modifications will be documented as Statistical Analysis Modification Requests.

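### Does the SAP drop the table of abnormal laboratory values that the protocol promises?

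*SAP*

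**What the plan says.** **Laboratory data, protocol.** Section 13.5.3 asks for the investigator's overall interpretation and any clinically significant findings to be listed, and then adds: "All laboratory results will be listed and a table of all the abnormal values will be presented". Versions 2.0 and 3.0 have the same sentence. Laboratory tests are done at screening, and section 10.2 sets the second occasion: "The same analyses, with the exception of urine drug test and virology, will be performed at the final visit/ETV".

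**Laboratory data, SAP version 2.0.** Section 4.11.3 opens with "Summaries will be presented for the overall interpretation of the laboratory data" and gives numbers and percentages of subjects in the three interpretation categories. It then plans by-subject listings of all laboratory data with reference ranges: "All values outside the clinical reference ranges will be flagged in the data listings". The flag is L or H. On clinically significant findings, section 3.2.3.2 says: "All CS abnormalities after the screening visit will be recorded as AEs". Section 4.11.1 then plans, among other tables, "A summary of TEAEs by SOC, and PT". Section 4.13, where changes to the planned analysis would be declared, contains only NA.

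**Vital signs.** Protocol section 13.5.4 asks for listings and descriptive statistics. SAP section 4.11.4 provides both for the measured values. SAP section 4.2 defines a baseline for each period, but 4.11.4 does not use it for a change-from-baseline summary.

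**The concern.** The protocol names a specific safety output and the SAP section on that topic does not contain it. Version lag is no explanation. The SAP says it was written from Protocol Version 2.0 of 18 April 2019, and that version already had the sentence.

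The two documents even look reversed. The protocol lists the interpretation and tabulates the abnormal values, whereas the SAP tabulates the interpretation and only lists the values. The SAP's laboratory tables name no parameter, so they cannot stand in for the promised table. With NA in section 4.13, this could be read as a protocol commitment dropped without notice.

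Safety and tolerability is the secondary end-point, and laboratory parameters are among its named variables. If the table were lost, a reader wanting to know which analytes went out of range would have to search the full listing. The same thinking prompts the vital-sign question: a per-period baseline is defined, yet no planned output shows within-subject change.

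**Working it through.** The plan has no figure to reproduce here, because nothing is tested and no sample size was calculated. The check is to follow each kind of abnormal result through the planned outputs.

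| Kind of out-of-range result | Flagged listing (SAP 4.11.3) | Interpretation counts (SAP 4.11.3) | Adverse event tables (SAP 4.11.1) |
|---|---|---|---|
| After screening, clinically significant | yes | yes | yes, through SAP 3.2.3.2 |
| After screening, not clinically significant | yes | yes | no |
| Screening, not clinically significant | yes | yes | no |
| Screening, clinically significant | yes | yes | no; exclusion criterion 3 (protocol 8.3) should keep such subjects out when the value indicates illness |

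Every row reaches the flagged listing. The second and third rows have no table that names the parameter, and this is the whole of the gap.

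**Size of the listing to be searched.** Planned subjects: 24 (protocol 13.2). Scheduled laboratory occasions: 2, screening and final or early termination visit (protocol 10.2 and the study schedule). 24 × 2 = 48 scheduled subject-visits at most, plus any repeats. How many results will be abnormal cannot be known in advance.

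**What the promised table would add.** It would show subject, cohort, visit, parameter, value, range and flag for the out-of-range results. The planned listings already hold the results, visits, ranges and flags by subject, so the table amounts to keeping the rows marked L or H. No new data or derivation is needed.

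**Whether the SAP overrides the protocol.** The SAP's Introduction says it covers analysis details that the protocol does not provide. Read that way, silence in 4.11.3 leaves 13.5.3 standing, and NA in 4.13 fits with no change having been made. The revision history also mentions output shells, which are not among the documents and may include the table.

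**Superseded SAP.** Version 1.0, section 4.11.3, planned "A summary of value and changes from baseline for each laboratory parameter by time point" and a shift table. Neither is a table of all abnormal values, so their removal does not bear on the commitment. The revision history explains that version 1.0 rested on a draft protocol and not on the case report form.

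**Vital signs.** Post-baseline times from protocol 10.1.2:

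- Period 1: day 1 at 2 h and day 5 at 96 h = 2.
- Period 2: day 8 at 2 h (1) + days 10 to 13 pre-dose (4) + day 14 pre-dose and 2 h (2) + day 18 at 96 h (1) = 8.
- Total 2 + 8 = 10.

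A change table would have 10 × 3 measures × 2 cohorts = 60 rows. It would be built from 10 × 3 × 16 = 480 individual changes at the floor of 8 completers per cohort, or 10 × 3 × 24 = 720 if all complete. These figures count an output that neither current document promises. They do not measure an error.

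**The case for a change.** The best case for a change is that the SAP says it outlines the programming specifications for tables, listings and figures, and 4.11.3 does set out the laboratory outputs. A programmer working from that section alone would not produce the abnormal-values table. The sponsor could close the gap with one filtered table, or with one sentence in 4.13 saying that the flagged listing replaces it.

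The textual point stands: the SAP does not repeat the table, and the interpretation counts are no substitute. It is also fair that results judged not clinically significant would have no parameter-level table if the protocol sentence were overlooked.

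What does not stand is the step from there to a defect in the plan. To call the table dropped assumes a decision that the documents do not show, since the protocol sentence can be read as still binding. If it were overlooked, the effect would be one of layout: the same flagged values in a longer listing.

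On vital signs, the mean change can be read from the raw means when the same subjects contribute at both times, but the spread and extremes of individual change cannot. They can be derived from the planned listing. Showing them would be a reasonable extra, but 4.11.4 already meets protocol 13.5.4.

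**Conclusion.** No change to the plan is needed. There is a minor difference in wording between protocol 13.5.3 and SAP 4.11.3, and an analyst can resolve it by producing the protocol's table from the flagged rows of the planned listing. Following the SAP exactly as written would lose no value, reference range or flag. Clinically significant findings after screening would still reach the adverse event tables. No safety result would differ, and the primary pharmacokinetic analysis does not use these data. The material is at most 48 scheduled subject-visits.

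This rests on two conditions: the listing is produced in full with its flags, and investigators record clinically significant abnormalities as adverse events. Both are written into the SAP. The vital-sign suggestion is a preference about presentation in a descriptive study without placebo, and it contradicts nothing in either document.
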